## 10. Risks to Subjects

Possible documented risks to using virtual reality include seizures; loss of awareness; eye strain; eye or muscle twitching; involuntary movements; altered, blurred, or double vision or other visual abnormalities; dizziness; disorientation; impaired balance; impaired hand-eye coordination; excessive sweating; increased salivation; nausea; lightheadedness; discomfort or pain in the head or eyes; drowsiness; fatigue; and/or motion sickness.

About 1 in 4000 may have severe dizziness, seizures, eye or muscle twitching or blackouts triggered by light flashes or patterns, and this may occur while they are watching TV, playing video games or experiencing virtual reality, even if they have never had a seizure or blackout before or have no history of seizures or epilepsy. Such seizures are more common

in children and young people under the age of 20. These risks are generally associated with prolonged use and with the complete VR systems which entail large, fitted headsets and full body utilization. The VR hardware being used for this study is a reductive version (a hand-held View-Master with a smartphone), the participants will be seated for the duration and the experiences will last 10-15 minutes. The participant will be in complete control and can set down the View-Master at any time as well as choose to discontinue the experience.

#### **11. Potential Benefits to Subjects**

There are no known benefits to using virtual reality prior to a medical procedure; however, it is possible that participation in the study could reduce preprocedural anxiety for the intervention group.

#### **12. Provisions to Protect the Privacy Interests of Subjects**

Study personnel will conduct initial phone calls to patients and participants during routine business hours, unless otherwise requested by the recipient. Study personnel will routinely inquire if it is a good time to talk and if told it is not will ask for another, more convenient time to talk.

In person meetings will take place within Spectrum Health facilities and all visits will be conducted in private spaces, unless otherwise requested by the participant. The baseline visits will be conducted in a setting where the equipment will be available and its use appropriate. The preprocedure visit will be conducted in the participant's private Prep/Recovery room in the MHC Cath Lab. Study personnel will remain cognizant of others (staff, family, and friends) and will assess the participant for cues of distress or discomfort. If deemed necessary, study personnel may suggest to staff, family or friends that a few minutes of privacy is required to conduct the study activities.

#### **13. Provisions to Maintain the Confidentiality of Data**

Primary data related to this study will be maintained onsite at Spectrum Health in secure facilities or on secure Spectrum Health servers. Only study personnel will have access to the primary data. A single Excel spreadsheet correlation tool (excluding EDC/REDcap) will be maintained associating the participant's name and DOB with her or his study ID; all other research tools and research documents will include only the subject's study ID. The correlation tool and other research documents will be stored on the "M Drive" in a study specific folder to which only Spectrum Health research personnel should have access.

REDcap is a Spectrum Health licensed and supported secure web application for building and managing online surveys and databases. Within REDcap, the VR-THEIA study will be accessible only to current, SH IRB approved study personnel. The VR-THEIA database will contain PHI.

If any data are shared with external sites for analysis, appropriate / applicable agreements will be executed (e.g., data use and/or research collaboration agreements) between involved parties prior to the sharing of those data. The shared data will be de-identified to the fullest extent possible.

#### **14. Cost to Subjects**

Participants will not incur any costs for participation in this study.

#### **15. Consent Process**

Potential participants will be identified via electronic record review. Those appearing to meet inclusion / exclusion criteria will be called over the phone. Study personnel will identify

themselves, explain their affiliation and purpose for calling. If the patient has time to talk, the study will be introduced. If the patient is interested in hearing the details, study personnel will proceed with explaining the details of the study. If the patient is interested in participating, study personnel will ask if a PDF of the consent form can be emailed or faxed directly (due to likely time constraints between the time the patient is identified and procedure date); if yes, study personnel will send the consent. If no, study personnel will review all sections of the consent over the phone.

In the setting of sending the CF electronically, a follow up call will be conducted to learn the patient's decision. In the setting of live review, the patient will be given the option to schedule a follow up call in order to allow them private time to consider participation. It will be explicitly requested that the CF not be signed prior to the baseline/enrollment visit. All interested patients will be scheduled for an enrollment/baseline visit with study personnel at a Spectrum Health outpatient office wherein the CF will be reviewed again in full and written consent will be obtained prior to the commencement of any study activities.

## **16. Vulnerable Populations**

No vulnerable populations will be included for participation in this study.

## **17. Sharing of Results with Subjects**

There are no plans to formally share the results of this study with the participants. If participants request information post participation, any published results would be shared.

## **19. Appendices**

### **Appendix A – Cardiac Catheterization Information Sheet**

82058

## Having Cardiac Catheterization

You may have had chest pain (angina), dizziness, or other symptoms of heart trouble. To help diagnose your problem, your healthcare provider may advise a cardiac catheterization. This is a procedure that looks for a blockage or narrow area in the arteries around the heart. These can cause chest pain or a heart attack if not treated.

This common procedure may also be used to treat a heart problem. It may be done as a planned procedure if you have had chest pain in the past. Or it may be done right away to treat a suspected heart attack.

[figure not shown]
### Before the procedure

- Tell your healthcare team what medicines you take and about any allergies you have.
- Don't eat or drink anything after midnight the night before the procedure, or as instructed by your healthcare team.

### During the procedure

- Hair may be trimmed where the catheter will be inserted.
- You may be given medicine to relax before the procedure.
- You will receive a local anesthetic to prevent pain at the insertion site.
- A healthcare provider inserts a tube called a sheath into a blood vessel in your groin or arm.
- Through the sheath, a long, thin tube called a catheter is placed inside the artery. The catheter is then guided toward your heart.
- To do different tests or check other parts of the heart, the healthcare provider inserts a new catheter or moves the catheter or X-ray machine. For some tests, a contrast dye is injected through the catheter.

### Catheter placement

**The catheter may be placed in the arm or the groin.**

### After the procedure

- Your healthcare providers will tell you how long to lie down and keep the insertion site still.
- If the insertion site was in your groin, you may need to lie down with your leg still for 2 or more hours. If a suture or closure device such as a collagen plug is used on the artery site to close the site, you may be able to move sooner. This depends on any bleeding that occurs.
- A nurse will check the insertion site and your blood pressure.
- You may be asked to drink fluid to help flush the contrast liquid out of your system.
- Have someone drive you home from the hospital.
- It's normal to find a small bruise or lump at the insertion site. This should go away within a few weeks.

### When to call your healthcare provider

Call your healthcare provider right away if you have any of the following:

- Chest pain (angina)
- Pain, swelling, redness, bleeding, or fluid leaking at the insertion site
- Severe pain, coldness, or a bluish color in the leg or arm that held the catheter
- Blood in your urine, black or sticky stools, or any other kind of bleeding
- Fever of 100.4°F (38.0°C) or higher, or as advised by your healthcare provider

© 2000-2016 The StayWell Company, LLC. [name]. All rights reserved. This information is not intended as a substitute for professional medical care. Always follow your healthcare professional's instructions.

## Appendix B – State-Trait Anxiety Inventory (STAI)

**SELF-EVALUATION QUESTIONNAIRE STAI Form Y-1**

Please provide the following information:

Name \_\_\_\_\_ Date \_\_\_\_\_ S \_\_\_\_\_  
Age \_\_\_\_\_ Gender (Circle) M F T \_\_\_\_\_

**DIRECTIONS:**

A number of statements which people have used to describe themselves are given below. Read each statement and then circle the appropriate number to the right of the statement to indicate how you feel *right now*, that is, *at this moment*. There are no right or wrong answers. Do not spend too much time on any one statement but give the answer which seems to describe your present feelings best.

	1	2	3	4
1. I feel calm .....	1	2	3	4
2. I feel secure .....	1	2	3	4
3. I am tense .....	1	2	3	4
4. I feel strained .....	1	2	3	4
5. I feel at ease .....	1	2	3	4
6. I feel upset .....	1	2	3	4
7. I am presently worrying over possible misfortunes .....	1	2	3	4
8. I feel satisfied .....	1	2	3	4
9. I feel frightened .....	1	2	3	4
10. I feel comfortable .....	1	2	3	4
11. I feel self-confident .....	1	2	3	4
12. I feel nervous .....	1	2	3	4
13. I am jittery .....	1	2	3	4
14. I feel indecisive .....	1	2	3	4
15. I am relaxed .....	1	2	3	4
16. I feel content .....	1	2	3	4
17. I am worried .....	1	2	3	4
18. I feel confused .....	1	2	3	4
19. I feel steady .....	1	2	3	4
20. I feel pleasant .....	1	2	3	4

**SELF-EVALUATION QUESTIONNAIRE**

STAI Form Y-2

Name \_\_\_\_\_ Date \_\_\_\_\_

**DIRECTIONS**

A number of statements which people have used to describe themselves are given below. Read each statement and then circle the appropriate number to the right of the statement to indicate how you generally feel.

	NEVER	SOMETIMES	ALMOST ALWAYS
21. I feel pleasant.....	1	2	3
22. I feel nervous and restless.....	1	2	3
23. I feel satisfied with myself.....	1	2	3
24. I wish I could be as happy as others seem to be.....	1	2	3
25. I feel like a failure.....	1	2	3
26. I feel rested.....	1	2	3
27. I am "calm, cool, and collected".....	1	2	3
28. I feel that difficulties are piling up so that I cannot overcome them.....	1	2	3
29. I worry too much over something that really doesn't matter.....	1	2	3
30. I am happy.....	1	2	3
31. I have disturbing thoughts.....	1	2	3
32. I lack self-confidence.....	1	2	3
33. I feel secure.....	1	2	3
34. I make decisions easily.....	1	2	3
35. I feel inadequate.....	1	2	3
36. I am content.....	1	2	3
37. Some unimportant thought runs through my mind and bothers me.....	1	2	3
38. I take disappointments so keenly that I can't put them out of my mind.....	1	2	3
39. I am a steady person.....	1	2	3
40. I get in a state of tension or turmoil as I think over my recent concerns and interests.....	1	2	3

## Appendix C – Wellness Self Assessments

Subject ID:

### **Pre VR Experience Wellness Self-Assessment**

Please identify if you are currently experiencing any of the following and rate the degree of severity of the symptom(s) on a scale from 1 (mild) – 5 (severe):

1. Headache:

No       Yes

1                    2                    3                    4                    5

2. Altered/Blurred/Double Vision:

No       Yes

1                    2                    3                    4                    5

3. Nausea:

No       Yes

1                    2                    3                    4                    5

4. Dizziness/Disorientation:

No       Yes

1                    2                    3                    4                    5

5. Fatigue:

No       Yes

1                    2                    3                    4                    5

Subject ID:

### **Post VR Experience Wellness Self-Assessment**

Please identify if you are currently experiencing any of the following and rate the degree of severity of the symptom(s) on a scale from 1 (mild) – 5 (severe):

1. Headache:

No       Yes

1                    2                    3                    4                    5

2. Altered/Blurred/Double Vision:

No       Yes

1                    2                    3                    4                    5

3. Nausea:

No       Yes

1                    2                    3                    4                    5

4. Dizziness/Disorientation:

No       Yes

1                    2                    3                    4                    5

5. Fatigue:

No       Yes

1                    2                    3                    4                    5

Subject ID:

### **Retrospective VR Experience Wellness Self-Assessment**

Please identify if you recall any of the following within 24 hours after your VR experience and rate the degree of severity of the symptom(s) on a scale from 1 (mild) – 5 (severe):

1. Headache:

No       Yes

1                    2                    3                    4                    5

2. Altered/Blurred/Double Vision:

No       Yes

1                    2                    3                    4                    5

3. Nausea:

No       Yes

1                    2                    3                    4                    5

4. Dizziness/Disorientation:

No       Yes

1                    2                    3                    4                    5

5. Fatigue:

No       Yes

1                    2                    3                    4                    5

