- The participant will be shown the individual components of the VR system (View-Master with smartphone inserted; external speaker for audio projection; monitor for study staff to observe what the participant is experiencing), be given instructions on how to use the device and encouraged to ask questions.
- Once the participant indicates she or he is ready, they'll be asked to begin the VR experience. Study personnel will stay in the room with the participant for the entire duration and will be viewing on the monitor what the participant is experiencing virtually. Study personnel will provide guidance and answer questions regarding the technology and its use but will not answer questions regarding the facilities, prep, procedure or recovery (this will be explained prior to starting the VR experience).
- When the participant indicates she or he is finished with the VR experience and has had a few minutes to orient, the wellness self-assessment will be administered again.
- Participants will be thanked for their participation (and provided a gift card) and remaining study activities will be reviewed.

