### ***Visit 2 – Procedure Day***

Study personnel will meet participants in their Prep/Recovery room prior to their procedure and the STAI assessment will be administered to all. A Retrospective Wellness questionnaire will be administered to the VR intervention group only in order to assess for any longer-term adverse effects (e.g., headache lasting several hours) of the VR experience. Postprocedure, a patient preparedness survey will be administered to all participants. All participants will again be thanked for their participation, all questions will be answered and their study participation will conclude.

All of the above activities except for standard procedural education will be research related. The average study participation time frame for all participants will be less than 1 month.

The data collected for this study entails the State-Trait Anxiety Inventory results, wellness self-assessments results, preparedness survey results and meta-data results.

e. Data Management

The data collected for this study will comprise of survey results (State-Trait Anxiety Assessment; VR related wellness assessments; and a preparedness assessment) as well as demographic and medical history data (for general reporting purposes). The data will be collected directly from participants using paper tools, where after the responses will be entered into an electronic data capture (EDC) system. The study EDC will be housed on secure Spectrum Health servers and the paper documents will be stored in secure Spectrum Health facilities.

f. Withdrawal of Subjects

Participants may change their minds at any time and choose to withdraw from this study; however, there are no circumstances under which participants would be withdrawn without their consent.

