## 9. Statistical Plan

a. Sample Size Determination

Using G\*Power 3.1.5 and looking at two sample independent t-test for the primary endpoint, in order to detect an effect size of 0.5 between the groups at 90% power and using significance level of 0.05, 86 patients are required in each study group.

b. Statistical Methods

Categorical variables will be reported as count (frequency). Normally distributed continuous variables will be reported as mean  $\pm$  standard deviation and non-normally distributed continuous variables will be reported as median (interquartile range). To determine if there is a difference in the two groups demographic variables a two sample t-test will be used for normally distributed continuous variables, a Mann Whitney Test will be used for non-normally distributed continuous variables, and a Chi-square will be used for categorical variables unless assumptions aren't met then Fishers Exact test will be used. To compare the anxiety levels of the group of individuals randomized to VR and standard procedural education vs. standard procedural education alone an independent two sample t-test will be used. If assumptions aren't met then a Mann Whitney test will be used. To determine if there is a difference in anxiety before and after the use of VR a paired t-test will be used. If assumptions aren't met then a Wilcoxon Signed Rank test will be used. Significance will be assessed at an alpha of 0.05.

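### The retrospective wellness form is meant to find longer-lasting effects of VR, but no form records how long a symptom lasted, so its Yes answers give only an upper bound

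*Combined protocol and SAP*

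**What the plan says.** Section 8d, Visit 2 – Procedure Day, states who completes the form: "A Retrospective Wellness questionnaire will be administered to the VR intervention group only". It gives one purpose: "in order to assess for any longer-term adverse effects (e.g., headache lasting several hours) of the VR experience". The protocol's own example of a longer-term effect is thus defined by how long it lasts.

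The form itself, the Retrospective VR Experience Wellness Self-Assessment in Appendix C, asks: "Please identify if you recall any of the following within 24 hours after your VR experience and rate the degree of severity". Five symptoms follow (headache, vision, nausea, dizziness, fatigue), each with No/Yes and a 1–5 severity scale. The form has no other items.

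The only earlier record after exposure is the post-VR form. Section 8d, Visit 1 – Baseline, places it at the point when the participant "has had a few minutes to orient, the wellness self-assessment will be administered again". Its instruction begins "Please identify if you are currently experiencing any of the following and rate the degree of severity of the symptom(s", so it describes that moment only.

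Section 9b (Statistical Methods) gives no analysis of the wellness forms and no rule for separating brief from lasting symptoms.

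**The concern.** The form has a single stated job, which turns on duration, and it does not ask about duration. Its recall period begins as soon as VR ends, so it also takes in the short-lived symptoms that the post-VR form is there to capture. A Yes on procedure day may mean a headache that went on all evening, or one that was gone before the participant left the visit.

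What is at stake is the report of VR's tolerability. Section 10 lists dizziness, nausea, visual disturbance and fatigue among the possible risks, and any published statement on lasting effects would rest on this form. If the Yes answers are reported under the label the protocol gives them, brief symptoms will be presented as longer-term ones.

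**Working it through.** **Inputs.** Purpose and timing of the retrospective form: section 8d, Visit 2. Content of the two post-exposure forms: Appendix C. Timing of the post-VR form: section 8d, Visit 1. One assumption is added: the post-VR form is completed about 5 minutes after VR ends (the protocol gives no exact time). Recall is taken as accurate.

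**Step 1. What each symptom course would record.** The post-VR form is Yes if the symptom is present at about 5 minutes. The retrospective form is Yes if the symptom began within 24 hours.

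| Course of the symptom | Post-VR form | Retrospective form |
|---|---|---|
| Starts with VR, clears in 2 min | No | Yes |
| Starts with VR, clears in 10 min | Yes | Yes |
| Starts with VR, lasts 8 h | Yes | Yes |
| Starts with VR, lasts 36 h | Yes | Yes |
| Starts at 3 h, lasts 5 min | No | Yes |
| Starts at 3 h, lasts 8 h | No | Yes |
| Starts at 26 h, lasts 8 h | No | No |

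The retrospective form alone gives Yes for every course that starts within 24 hours, whatever its length. Pairing the forms does not help. Yes/Yes covers 10 minutes, 8 hours and 36 hours. No/Yes covers a symptom that cleared in 2 minutes, a brief late one and an 8-hour late one. Severity does not separate them, since a brief symptom can be severe and a long one mild.

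**Step 2. What the Yes proportion estimates.** For one symptom, let L be the proportion of VR participants with a lasting symptom that began within 24 hours, and T the proportion with only a brief one. Then

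proportion answering Yes = L + T, so L ≤ proportion answering Yes.

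The form yields only the sum. L may lie anywhere from 0 to the observed proportion. The excess is T, which neither form identifies: the same inequality applies separately within the Yes/Yes and No/Yes groups. The documents give no symptom rates, so the excess cannot be sized in advance.

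**Step 3. How many participants.** All of the VR arm: 86 per group (section 9a), up to about 200 / 2 = 100 if enrolment reaches the limit in section 8a with 1:1 allocation. Duration is recorded for none of them.

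**Step 4. The plan's own figure.** The only computed design figure is 86 per group. A two-sided two-sample t-test with effect size 0.5, alpha 0.05 and 90% power needs 85.03, rounded up to 86, where power is 0.903. It reproduces and plays no part in this point.

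**The case against.** The best defence is that the form is a screen. Every lasting symptom that began within 24 hours produces a Yes, so a No excludes a recalled one, and few Yes answers would be reassuring. This stands, and it is why the result is an upper bound and not worthless. But a screen needs a follow-up for positives, and the documents describe no further question after a Yes.

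Second, the 24-hour limit is defensible. The protocol's example is measured in hours and fits well inside it. The form goes to the VR arm only, so a longer window would gather background headache and fatigue in patients awaiting catheterization, with no control-arm figure against which to judge them. This stands too: the limit is not what makes the form fail, and it should stay.

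Third, the data are descriptive. Wellness scores are not among the endpoints in section 8c, and enrolment had begun by this version (section 8d, Randomization, speaks of the rest of the study), so a revised form would leave two instruments in one arm. Both are true. They limit the weight of the point and add to the cost of the fix, but they do not make the present form measure duration.

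**Conclusion.** The point holds as a minor one. The forms as written cannot separate lasting from transient symptoms in any VR participant. With accurate recall, the Yes proportion is an upper bound on lasting effects that began within 24 hours, and no more. The only other assumption, the 5-minute timing of the post-VR form, decides which brief symptoms show as No/Yes rather than Yes/Yes; it does not change the conclusion.

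Three stronger readings are tempting, and the documents do not support them:

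- A reader might infer that the error has an unknown direction, since symptoms starting after 24 hours are missed. For symptoms starting within 24 hours the direction is known: too high. Nothing in the documents suggests later onset after a seated exposure of 10–15 minutes on simple equipment (section 10).
- A reader might take No followed by Yes as proof of late onset. A symptom that cleared before the post-VR form was completed gives the same pair.
- A reader might want a factor by which lasting effects are overstated. Any such factor would only restate assumed rates.

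The STAI comparison, the preparedness comparison and the sample size are untouched.

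**What to change.** For each Yes on the retrospective form, add three items:

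- when the symptom started: during or right after VR, or later;
- about how long it lasted: under 1 h, 1–6 h, 6–24 h, or over 24 h;
- whether it is still present.

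Keep the 24-hour window for onset. State in section 9b which duration categories will count as lasting, and report lasting and transient symptoms separately. For participants who completed the present form, report Yes as any symptom recalled within 24 hours of VR, not as a longer-term effect.

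The cost is a one-page form revision, a few database fields and an amendment. No visit is added. Duration will be available only for participants enrolled after the change, so the two groups have to be tabulated separately. If the form is not revised, the reporting rule for the present form should still be adopted for everyone; it requires no new data.
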